## 9.2. PROTOCOL DEVIATIONS

The number and percentage of participants with important protocol deviations will be summarized overall and by cohort based on the all participants analysis set, overall and by protocol deviation category. The number and percentage of participants with exclusionary protocol deviations for the immunogenicity analysis set will also be provided overall and by cohort. Protocol deviation categories are defined in a separate PD plan.

A listing of important protocol deviations identified by the study team will be provided.

## 10. DEMOGRAPHIC AND OTHER BASELINE CHARACTERISTICS

The following demographic and other baseline characteristics will be reported for this study:

- Age (years) – calculated relative to date of consent
- Age groups (refer to [Section 7.6](#))
- Sex
- Race
- Ethnicity
- Country
- Weight (kg)
- Height (cm)
- Body Mass Index (BMI) (kg/m^2)

Continuous demographic and other baseline characteristics will be summarized using descriptive statistics overall and by cohort based on the SAF analysis set. For categorical demographic and other baseline characteristics, number and percentage of subjects in each category will be provided overall and by cohort based on the SAF analysis set. No statistical testing will be carried out for demographic or other baseline characteristics.

## 10.1. DERIVATIONS

BMI, in kg/m^2, will be calculated as follows:

- BMI (kg/ m^2) = weight (kg)/ [height (m)]

## 11. SURGICAL AND MEDICAL HISTORY

Surgical and medical history are defined as any surgeries that happened before the first dose of study intervention and any medical conditions/diseases that started and stopped before the first dose of study intervention.

Surgical and medical history will be coded using the Medical Dictionary for Regulatory Activities (MedDRA), version 23.0 or higher, and will be summarized by System Organ Class (SOC) and Preferred Term (PT) overall and by cohort based on the SAF analysis set. A subject having more than one surgery/medical condition/disease within the same SOC/PT will be counted only once for that SOC or PT.

All surgical and medical history will be listed.

Baseline co-morbidities solicited on the eCRF page will be summarized separately from medical histories overall and by cohort based on the SAF.

## 12. CONCOMITANT ILLNESSES

Concomitant conditions/illnesses are defined as any medical conditions/illnesses that started before the first dose of study intervention AND were ongoing at the time of the first dose of study intervention or ended on the first dose of study intervention.

Concomitant conditions/illnesses will be coded using the MedDRA, version 23.0 or higher, and will be summarized by SOC and PT overall and by cohort based on the SAF analysis set. A participant having more than one medical condition/illness within the same SOC or PT will be counted only once for that SOC or PT.

All concomitant conditions/illnesses will be listed.

## 13. MEDICATIONS

Prior medications are defined as any medication that started and stopped prior to the first dose of study intervention.

Concomitant medications are defined as:

- Any medication that started before the first dose of study intervention AND was ongoing at the time of the first dose of study intervention or ended on the date of first dose of study intervention.
- Any medication that started on or after the first dose of study intervention.

Partially or completely missing medication start and stop dates will be handled as described in [APPENDIX 1](#).

All medications will be coded using the World Health Organization (WHO) Drug Global dictionary, version B3 March 2020 or later. The dictionary will be updated when a new dictionary version becomes available to IQVIA.

Prior and concomitant medications will be summarized by Anatomical Therapeutic Class (ATC) level 2 and preferred drug name overall and by cohort based on the SAF analysis set. A participant having more than one medication within the same ATC Level 2 or preferred drug name will be counted only once for that ATC Level 2 or preferred drug name.

All prior and concomitant medications will be listed.

## 14. EXPOSURE TO STUDY DRUG

Due to the simplicity of dosing for this study, exposure is summarized in the Disposition table. No other summary will be reported. A listing will provide exposure information for all participants in the SAF analysis set.

Report of overdose and medication error, if any, will be listed for the SAF analysis set.

## 15. COMPLIANCE WITH STUDY DRUG

Compliance will not be calculated since participants are vaccinated within clinic.

A summary of the interval between doses 1 and 2, doses 2 and 3 and doses 1 and 3 of study intervention will be provided. The dosing interval between dose X and dose Y is calculated as the date of dose Y – date of dose X +1 for all participants who received dose X and Y of study intervention. This analysis will be based on the SAF. The

summary based on IAS for the study will also be repeated by age group (18-64 years and  $\geq 65$  years).

## 16. IMMUNOGENICITY ENDPOINTS

Unless otherwise indicated, all immunogenicity summaries and figures will be presented by cohort (including the pooled immunocompromised cohort) and visit, when appropriate, based on the immunogenicity analysis set.

For all immunogenicity endpoints, participants will be censored at the date of first positive PCR test for SARS-CoV-2 infection/non-study COVID-19 vaccine administration/exclusionary restricted medication, whichever occurs first, such that data from all visits after the date of first positive PCR test for SARS-CoV-2 infection/non-study COVID-19 vaccine administration/exclusionary restricted medication will be excluded from derivations and all by-visit summaries. All immunogenicity data regardless of censoring will be listed for all participants, with all censored assessments flagged.

For summaries over time, participants who do not receive dose 2 of study intervention will be excluded from all time points post dose 2. Participants who do not receive dose 3 of study intervention will be excluded from all time points post dose 3.

All participants will be assessed for serum samples for SARS-CoV-2 serology testing.

The immunogenicity primary endpoints are:

- Post-treatment GMTs and GMFRs from day of dosing baseline value to 28 days post dose 1 and dose 2 in SARS-CoV-2 S antibodies.
- Proportion of participants who have a post-treatment seroresponse ( $\geq 4$ -fold rise in titres from day of dosing baseline value to 28 days post dose 1 and dose 2) for the S antibodies.
- Post-treatment GMTs and GMFRs from day of dosing baseline value to 28 days post dose 1 and dose 2 in SARS-CoV-2 neutralizing antibodies (pseudo-neutralization assay)
- Proportion of participants who have a post-treatment seroresponse ( $\geq 4$ -fold rise in titres from day of dosing baseline value to 28 days post dose 1 and dose 2) as measured by SARS-CoV-2 neutralizing antibodies (pseudo-neutralization assay)

The immunogenicity secondary endpoints are:

- Ratio of post-treatment GMTs at 28 days post second dose in SARS-CoV-2 S antibodies between each immunocompromised cohort (including the pooled immunocompromised cohort) and immunocompetent participants.
- Difference in proportion of participants who have a post-treatment seroresponse ( $\geq 4$ -fold rise in titres from day of dosing baseline value to 28 days post second dose) to the S antibodies between each immunocompromised cohort (including the pooled immunocompromised cohort) and immunocompetent participants.
- Ratio of post-treatment GMTs at 28 days post second dose in SARS-CoV-2 neutralizing antibodies (pseudo-neutralization assay) between each immunocompromised cohort (including the pooled immunocompromised cohort) and immunocompetent participants.
- Difference in proportion of participants who have a post-treatment seroresponse ( $\geq 4$ -fold rise in titres from day of dosing baseline value to 28 days post second dose) as measured by SARS-CoV-2 neutralizing antibodies (pseudo-neutralization assay) between each immunocompromised cohort (including the pooled immunocompromised cohort) and immunocompetent participants.
- Post-treatment GMTs and GMFRs from day of dosing baseline value to 28 days post dose 3 in SARS-CoV-2 S antibodies for each immunocompromised cohort (including the pooled immunocompromised cohort).
- Proportion of participants who have a post-treatment seroresponse ( $\geq 4$ -fold rise in titres from day of dosing baseline value to 28 days post dose 3) in the S antibodies for each immunocompromised cohort (including the pooled immunocompromised cohort).
- Post-treatment GMTs and GMFRs from day of dosing baseline value to 28 days post dose 3 in SARS-CoV-2 neutralizing antibodies (pseudo-neutralization assay) for each immunocompromised cohort (including the pooled immunocompromised cohort).
- Proportion of participants who have a post-treatment seroresponse ( $\geq 4$ -fold rise in titres from day of dosing baseline value to 28 days post dose 3) as measured by SARS-CoV-2 neutralizing antibodies (pseudo-neutralization assay) for each immunocompromised cohort (including the pooled immunocompromised cohort).
- Ratio of post-treatment GMTs at 28 days post third dose in SARS-CoV-2 S antibodies between each

immunocompromised cohort (including the pooled immunocompromised cohort) and post-treatment GMTs at 28 days post second dose in SARS-CoV-2 S antibodies in immunocompetent participants.

- Difference in proportion of participants who have a post-treatment seroresponse ( $\geq 4$ -fold rise in titres from day of dosing baseline value to 28 days post third dose [second dose for immunocompetent participants]) to the S antibodies between each immunocompromised cohort (including the pooled immunocompromised cohort) and immunocompetent participants.
- Ratio of post-treatment GMTs at 28 days post third dose in SARS-CoV-2 neutralizing antibodies (pseudo-neutralization assay) between each immunocompromised cohort (including the pooled immunocompromised cohort) and post-treatment GMTs at 28 days post second dose in SARS-CoV-2 neutralizing antibodies (pseudo-neutralization assay) in immunocompetent participants.
- Difference in proportion of participants who have a post-treatment seroresponse ( $\geq 4$ -fold rise in titres from day of dosing baseline value to 28 days post third dose [second dose for immunocompetent participants]) as measured by SARS-CoV-2 neutralizing antibodies (pseudo-neutralization assay) between each immunocompromised cohort (including the pooled immunocompromised cohort) and immunocompetent participants.

The supportive analysis to immunogenicity secondary endpoints are:

- Proportion of participants who have a post-treatment seroresponse ( $\geq 4$ -fold rise in titres from day of dosing visit 8 (pre-dose 3) value to 28 days post dose 3) in the S antibodies for each immunocompromised cohort (including the pooled immunocompromised cohort).
- Proportion of participants who have a post-treatment seroresponse ( $\geq 4$ -fold rise in titres from day of dosing visit 8 (pre-dose 3) value to 28 days post dose 3) as measured by SARS-CoV-2 neutralizing antibodies (pseudo-neutralization assay) for each immunocompromised cohort (including the pooled immunocompromised cohort).

The exploratory immunogenicity endpoints are:

- Post-treatment GMTs and GMFRs from day of dosing baseline value to 28 days post dose 3 in SARS-CoV-2 S antibodies in immunocompetent participants.
- Proportion of participants who have a post-treatment seroresponse ( $\geq 4$ -fold rise in titres from day of dosing baseline value to 28 days post dose 3) in the S antibodies in immunocompetent participants.

- Post-treatment GMTs and GMFRs from day of dosing baseline value to 28 days post dose 3 in SARS-CoV-2 neutralizing antibodies (pseudo-neutralization assay) in immunocompetent participants.
- Proportion of participants who have a post-treatment seroresponse ( $\geq$  4-fold rise in titres from day of dosing baseline value to 28 days post dose 3) as measured by SARS-CoV-2 neutralizing antibodies (pseudo-neutralization assay) in immunocompetent participants.
- Post-treatment GMTs and GMFRs from baseline value to 28 days post each dose in ChAdOx1 neutralizing antibodies
- Proportion of participants who have a post-treatment seroresponse ( $\geq$  4-fold rise in titres from Day 1 baseline value to 28 days post each dose) as measured by ChAdOx1 neutralizing antibodies
- Post-treatment GMTs and GMFRs from day of dosing baseline value to 28 days post each dose in SARS-CoV-2 RBD antibodies
- Proportion of participants who have a post-treatment seroresponse ( $\geq$  4-fold rise in titres from day of dosing baseline value to 28 days post each dose) to the RBD antibodies

The exploratory cell-mediated immune (CMI) response endpoint is:

- Intracellular cytokine staining and flow cytometry for B- and T-cell responses from day of dosing baseline to 14 days post each dose

Other exploratory assays for humoral and cellular immune responses may be performed based upon emerging safety, efficacy, and immunogenicity data and will be described in a separate document.

Pairwise correlations between anti-S, pseudo-neutralization, and ChAdOx1 nAb antibody titres, 28 days after Dose 1 and 28 days after Dose 2 will be explored.

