### 2.2. SECONDARY OBJECTIVES

The secondary safety objective is to characterize the reactogenicity and safety of a 3-dose primary vaccination series with AZD1222 with a 4-week dosing interval in SARS-CoV-2 naïve immunocompromised adults  $\geq 18$  years.

The immunogenicity secondary objectives are:

- To characterize the immunogenicity after a 3rd-dose in a 3 dose primary vaccination series with AZD1222 in immunocompromised adults  $\geq 18$  years.
- To describe the immunogenicity of a 2-dose primary vaccination with AZD1222 in adults  $\geq 18$  years with 4-week dosing interval between SARS-CoV-2 naïve participants with the below conditions compared to immunocompetent participants:
  - Solid organ transplant
  - Hematopoietic stem cell transplant
  - Solid organ cancer patients receiving cytotoxic chemotherapy

- Chronic inflammatory disorders
- Primary immunodeficiency
- Any immunocompromised condition, pooled populations above
- To describe the immunogenicity after the 3rd dose in a 3-dose primary vaccination series with AZD1222 in adults  $\geq 18$  years between SARS-CoV-2 naïve immunocompromised participants (see above conditions) compared to immunocompetent participants after a 2-dose primary vaccination.
- To describe the immunogenicity of the AZD1222 vaccination between 28 days post 3rd-dose compared to 28 days post 2nd-dose, in adults  $\geq 18$  years between SARS-CoV-2 naïve immunocompromised and immunocompetent participants.
- To characterize the immunogenicity after a 3rd-dose booster vaccination of AZD1222, administered 6 months after dose 1 of a 2-dose primary vaccination with AZD1222, in immunocompetent adults  $\geq 18$  years.

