### 7.1. SAMPLE SIZE CALCULATION

It is expected that approximately 360 participants will be enrolled (approximately 60 participants in each cohort). There is no statistical hypothesis testing planned for this study. Descriptive analyses will support evaluation of safety and immunogenicity.

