### **16.1.1. QUANTIFICATION OF ANTIBODY LEVELS**

SARS-CoV-2 S, RBD and nucleocapsid antibodies will be assessed quantitatively using a validated multiplexed MSD immunoassay at each scheduled visit as per protocol section 1.3. SARS-CoV-2 NAb will be measured using validated pseudoneutralization assays.

The antibody titre measurements will be summarized at each scheduled visit using geometric mean titre (GMT) and geometric mean fold rise (GMFR).

Descriptive statistics for GMTs and GMFRs will include number of participants, GMT, 95% confidence interval (CI), median, minimum and maximum.

The ratio of post-treatment GMTs values between each immunocompromised cohort and immunocompetent group will be presented with corresponding 95% confidence limits.

The GMT will be calculated as the antilogarithm of  $\Sigma$  (base 2 log transformed titre/n), i.e. as the antilogarithm transformation of the mean of the log-transformed titre, where n is the number of participants with titre information. The 95% CI will be calculated as the anti-logarithm transformation of the upper and lower limits for a two-sided CI for the mean of the log-transformed titres.

The fold rise is calculated as the ratio of the post-vaccination titre level to the pre-vaccination titre level, i.e., the baseline level (See [Section 6.2](#)). GMFR will be calculated as anti-logarithm of  $\Sigma$  (base 2 log transformed (post-vaccination titre/ pre-vaccination titre)/n). The 95% CIs for GMFR will be calculated similarly to those for GMT.

The antibody titre measurements will be presented in a data listing.

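### The dose-3/dose-2 GMT ratio is not restricted to participants with both titres, so selective loss can shift it in either direction

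*SAP*

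**What the plan says.** Section 2.2 of the SAP lists as a secondary objective "To describe the immunogenicity of the AZD1222 vaccination between 28 days post 3rd-dose compared to 28 days post 2nd-dose", in the immunocompromised and the immunocompetent.

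Table A (Section 2.4) has an estimand for it with two summaries: (a) a ratio of GMTs between the two times, and (b) a seroresponse summary based on a 4-fold rise from 28 days post dose 2 to 28 days post dose 3. Its population is anyone without an exclusionary deviation who had one or more doses. For participants who withdraw, miss a dose or take a restricted medication, only later data are treated as missing. A titre already obtained after dose 2 stays in.

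Section 16 sets inclusion separately for each time point. After dose 2, "participants who do not receive dose 2 of study intervention will be excluded from all time points post dose 2". After dose 3, "Participants who do not receive dose 3 of study intervention will be excluded from all time points post dose 3". Data after a first positive PCR, a non-study COVID-19 vaccine or an exclusionary medication are also removed. Section 16.1.1 takes the GMT from the mean log2 titre, "where n is the number of participants with titre information".

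Section 16 also defines a supportive proportion by a "fold rise in titres from day of dosing visit 8 (pre-dose 3) value to 28 days post dose 3) in the S antibodies" of 4 or more, with the same rule for neutralizing antibodies. It applies to each immunocompromised cohort and to the pooled group.

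**The concern.** Under these rules the post-dose-2 GMT and the post-dose-3 GMT are each computed on whoever has a usable titre at that visit. Anyone sampled 28 days after dose 2 who then misses dose 3, is censored, or has no sample 28 days after dose 3 counts in the first GMT and not in the second. If such people differ in titre from those who continue, the ratio moves even when the third dose does nothing.

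Nothing later in the SAP closes this for the GMT ratio:

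- Section 16 does not list the dose-3/dose-2 ratio as an endpoint.
- The GMFR in Section 16.1.1 refers to the value before the first dose, not to the post-dose-2 value.
- The confidence limits for a ratio of GMTs in Section 16.1.1 are described only between an immunocompromised cohort and the immunocompetent group.
- The repeated-measures model in Section 16.1.6, which has participant as a random effect, is dropped by the addendum.

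At stake is the estimate of how much a third dose raises titres within a group, which is what this secondary objective asks.

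**Working it through.** **The plan's own figure.** The only relevant figure is enrolment: "approximately 60 participants in each cohort" in 6 cohorts, 6 × 60 = 360, which agrees with Section 7.1. There is no precision calculation and no expected loss between doses 2 and 3.

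**Inputs that must be assumed.**
- d: the share of participants with a post-dose-2 titre who have no post-dose-3 titre; range 5% to 30%.
- Δ: how far the mean log2 titre of those lost lies below that of those who continue; range −1 (2-fold higher) to +2 (4-fold lower).

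**Formula, with no dose-3 effect.** Let μ be the mean log2 titre of those who continue.
- Post-dose-2 mean over all: (1 − d)μ + d(μ − Δ) = μ − dΔ.
- Post-dose-3 mean over those who continue: μ.
- Apparent GMT ratio: 2^(dΔ). On participants with both titres it is 2^0 = 1.00.

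**Results (true ratio 1.00 throughout).**

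| d | Δ = −1 | Δ = 0 | Δ = 1 | Δ = 2 |
|---|---|---|---|---|
| 5% | 0.97 | 1.00 | 1.04 | 1.07 |
| 10% | 0.93 | 1.00 | 1.07 | 1.15 |
| 20% | 0.87 | 1.00 | 1.15 | 1.32 |
| 30% | 0.81 | 1.00 | 1.23 | 1.52 |

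For example, d = 0.20 and Δ = 2 give 2^0.4 = 4^0.2 = 1.32. A simulation of that case (60 participants, 4,000 runs, between-participant SD 2 and within-visit SD 0.5 on the log2 scale) gave 1.32 for the all-available ratio and 1.00 for the paired ratio.

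**What the 4-fold-rise proportion already shows.** With no dose-3 effect and within-visit log2 SD s, the chance of an observed 4-fold rise is 1 − Φ(2/(s√2)): 0.2% for s = 0.5 and 2.2% for s = 0.7 (s assumed). It would therefore expose a third dose that does nothing. It gives no size of effect: a uniform 2-fold gain yields 1 − Φ(1/(s√2)), about 8% to 16% for the same s.

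**Where the mismatch can arise (target days in Tables D and E).**
- Immunocompromised: the 28-day post-dose-2 sample is the Visit 8 sample, taken before dose 3 at that same visit. The mismatch comes only from people sampled at Visit 8 who then miss dose 3 or have no usable titre at Visit 10, 28 days later.
- Immunocompetent: dose 2 is at day 29, so Visit 8 falls at day 29 + 28 = 57. Dose 3 is at day 183, which is 126 days later, and its sample comes 28 days after that. Loss and censoring have 154 days to act.

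**The case against.** The strongest reply is that the SAP already has paired summaries across dose 3. That is right. The supportive proportion in Section 16, the sensitivity estimand in Table A (population: three doses received), and part (b) of the dose-3-versus-dose-2 estimand all follow the same participant across the dose. A reader might infer from the visit-specific rules that no paired summary exists. The document does not support that; the gap is in the GMT ratio.

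Other objections, and what stands of them:

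- *The dose-3 exclusion rule is proper.* Agreed. Describing post-dose-3 titres in dose-3 recipients matches the three-dose estimands. The difficulty arises only when that GMT is divided by one from a wider set.
- *Most early losses leave both results.* Largely true for the immunocompromised, since someone lost before Visit 8 has no 28-day post-dose-2 titre either. It is less reassuring for the immunocompetent.
- *The direction is unknown.* True. A reader might infer that the ratio must be inflated. It may be unchanged or deflated.
- *The addendum limits the stakes.* In part. It drops between-arm comparisons, so immunocompromised after dose 3 against immunocompetent after dose 2 no longer matters here, and pairing could not help a comparison between different people. It also drops by-visit summary tables. It does not name the within-group ratio, and it otherwise defers to the main SAP.
- *The study is descriptive:* "There is no statistical hypothesis testing planned for this study". True, and loss with reasons and individual titres are also reported. A descriptive ratio still has to compare the same people if it is read as the change from dose 3.

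**Conclusion.** The concern holds for the GMT ratio of 28 days post dose 3 to 28 days post dose 2. As written, its population, inclusion rules and missing method allow numerator and denominator to rest on different people, so a stated secondary objective can be answered with vaccine effect and selective loss mixed together.

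The size cannot be derived from the SAP. Over the assumed ranges the ratio with no dose-3 effect runs from 0.81 to 1.52, and it is 1.00 if loss is unrelated to titre. The 1.32 illustration needs both a 20% loss and a 4-fold lower GMT in those lost. The risk is smaller for the immunocompromised and larger for the immunocompetent. With the much smaller sample described in the addendum, a few people can make up a large share: 2 of 10 is already 20%.

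This is a correction that should be made to one estimator. It is not evidence that the third-dose results as a whole are biased.

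**What to change.** Keep the all-available rows. In Table A, and in Section 16 or the addendum:

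1. State that the within-group dose-3/dose-2 GMT ratio uses participants with both a 28-days-post-dose-2 and a 28-days-post-dose-3 titre, after censoring.
2. List it as an endpoint for S and neutralizing antibodies. Compute it as the geometric mean of within-participant ratios, with a 95% CI back-transformed from the mean of the paired log2 differences.
3. Report it for the pooled immunocompromised group and for the immunocompetent group, with n and the GMT at both times on the same participants.
4. State in the addendum that this summary is retained.

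Optionally, on the same participants, cross-tabulate baseline-referenced seroresponse after dose 2 against after dose 3. The 4-fold-rise proportion puts someone already high after dose 2 in the same category as someone who never responded, so it cannot show how many dose-2 non-responders respond after dose 3. With the reduced enrolment these counts may be very small and should be read as such.

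Cost: a few lines of text, one extra table from existing titres, and a slightly smaller n for the ratio. No new data are needed.
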